9.2.4 Other outcomes

We will measure implementation-related outcomes to assess intervention fidelity. These will include the number of protocol-specified appointments (i.e., Spine Coach, physical therapist, or the Egoscue practitioner) scheduled and attended, the timing of visits and the length of the treatment course, which we originally expected to last 6 to 8 weeks.

9.3 Data Collection

Study data will be collected and managed using REDCap electronic data capture tools (50) hosted at Brigham and Women's Hospital. Data will be collected based on the schedule in Table 3. Study subjects will be contacted by email five business days prior to a survey being due for completion to be notified that the survey is available. If the survey is not completed they will be notified again three and five business days after the due date. Should the study subject still not complete the survey, they will have three phone attempts to be reached and guided through completion.

Table 3: Subject Reported Outcome Administration Schedule

Metric	Months After Enrollment													
	0	1	1.5	2	3	4	5	6	7	8	9	10	11	12
STarT Back Tool	x													
Healthcare Utilization Checklist		x		x	x		x		x		x		x	x
Oswestry Disability Index	x		x		x			x						x

EQ-5D	x		x					x						x
Self-Efficacy Questionnaire	x							x						x

10. Statistical considerations

10.1 Analysis plan

All analyses will be performed using intention to treat principles based on study arm with which a subject is assigned at study enrollment and regardless of whether or not all protocol steps have been completed. We will report means and frequencies of pre-randomization variables separately by study arm. Comparison of these values will be made with generalized estimating equations to adjust for the block and cluster randomized design.

Because cost data in healthcare is not normally distributed (32) due to significant zero data representing subjects for whom there is little to no cost, we will have to model the data accordingly. We will evaluate the two primary outcomes, total cost of care, using generalized estimating equations with gamma distributed errors and an identity link function which can account for a positively skewed distribution. Changes in ODI from baseline to three months will be compared for the treatment arms using generalized estimating with normally distributed errors and an identity link function. All models will adjust for age and sex, account for the cluster and block randomized study design and include fixed effects for the 3 different delivery networks that were used for recruitment. In secondary analyses, we will repeat our models adjusting for unmatched confounders that remained despite randomization. Our primary analyses will compare each of the two treatment arms separately with usual care (i.e., ICE compared with usual care and IPT with usual care). Because we are evaluating two primary

outcomes, we will use a Bonferroni-corrected two-tailed type 1 error of 0.025. Analysis of secondary outcomes will also be performed using generalized estimating equations with error distributions and link functions appropriate to the outcomes being evaluated.

Missing data will be accounted for using multiple imputation (51), which has been determined an adequate strategy to minimize both false positive and false negatives in clinical trials. We will perform 20 imputations using Proc MI in SAS with a fully conditional specification. The following variables will be used to perform the imputation: age, study arm, study site, clinic, sex, race/ethnicity, BMI, exercise frequency at baseline, education level, employment status, smoking status, other medical conditions at baseline, number of medications used for spine pain at baseline, length of pain at baseline, number of previous pain episodes, STarT back score, baseline ODI, baseline self-efficacy, baseline EQ-5D, and scores for patient-reported outcomes at every follow-up timepoints (ODI, cost, Lorig self-efficacy scale, and EQ-5D).

As resource utilization and ODI were collected at multiple time points, we will also evaluate non-missing cost and ODI data from each time point using a repeated measures design. In specific, we will use generalized estimating equations, with link functions and error distributions appropriate to the study outcomes, to assess changes in outcomes over the 12 months of follow-up, while accounting for correlations in the repeated measurements. For spine-related health spending, these analyses will be conducted using the time intervals at which raw data were collected as well as after converting estimates to evenly-spaced months. Because cost data in healthcare is not normally distributed with zero values for participants with no resource utilization during follow-up, we will winsorize estimated costs at the 95th

percentile in secondary analyses. We will report relative spending differences with confidence intervals and a two-tailed p value. As a sensitivity analysis, we will conduct a complete-case analysis on all non-missing values.

Exploratory analyses will be performed evaluating the effect of the interventions on cost in various strata of clinical interest, including age, sex, STarT Back risk group, location of pain, and whether or not this was the subject's first pain episode. We will also evaluate the percentage of subjects in each arm with a decrease in ODI of six points at three, six, and twelve months of follow-up.

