Because cost data in healthcare is not normally distributed (32) due to significant zero data representing subjects for whom there is little to no cost, we will have to model the data accordingly. We will evaluate the two primary outcomes, total cost of care, using generalized estimating equations with Poisson distributed errors and a log link function which can account for a positively skewed distribution. Changes in ODI from baseline to three months will be compared for the treatment arms using generalized estimating with normally distributed errors and an identity link function. All models will adjust for age and sex, account for the cluster and block randomized study design and include fixed effects for the 3 different delivery networks that were used for recruitment. In secondary analyses, we will repeat our models adjusting for unmatched confounders that remained despite randomization. Our primary analyses will compare each of the two treatment arms separately with usual care (i.e., ICE compared with usual care and IPT with usual care). Because we are evaluating two primary outcomes, we will use a Bonferroni-corrected two-tailed type 1 error of 0.025. Analysis of secondary outcomes will also be performed using generalized estimating equations with error distributions and link functions appropriate to the outcomes being evaluated.

Missing data will be accounted for using multiple imputation (51), which has been determined an adequate strategy to minimize both false positive and false negatives in clinical trials. We will perform 20 imputations using Proc MI in SAS with a fully conditional specification. The following variables will be used to perform the imputation: age, study arm, study site, clinic, sex, race/ethnicity, BMI, exercise frequency at baseline, education level, employment status, smoking status, other medical conditions at baseline, number of medications used for spine pain at baseline, length of pain at baseline, number of previous pain episodes, STarT back score, baseline ODI, baseline self-efficacy, baseline EQ-5D, and scores for patient-reported outcomes at every follow-up timepoints (ODI, cost, Lorig self-efficacy scale, and EQ-5D).

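### Protocol and SAP name different primary cost models, and the protocol's gamma choice has no mass at the zero costs it expects and no rule for keeping them

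*Combined protocol and SAP*

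**What the plan says.** Protocol section 10.1 (Analysis plan) explains that cost is not normally distributed "due to significant zero data representing subjects for whom there is little to no cost". For the primary cost outcome it then specifies "generalized estimating equations with gamma distributed errors and an identity link function which can account for a positively skewed distribution". Later in the section it again mentions "zero values for participants with no resource utilization during follow-up", and responds by winsorizing at the 95th percentile in secondary analyses.

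The SAP (Statistical considerations, section 1, Analysis plan) repeats the same text almost word for word, but for the same outcome it specifies "generalized estimating equations with Poisson distributed errors and a log link function which can account for a positively skewed distribution".

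Neither document gives a two-part model, an added constant, or a rule for keeping or excluding zero costs. Section 10.1 opens with "All analyses will be performed using intention to treat principles". SAS is named for the multiple imputation only; no routine is named for the GEE. No expected share of zeros is stated. Both documents say that relative spending differences will be reported.

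**The concern.** The protocol names zeros as the difficulty and then chooses a model that addresses skew. The gamma distribution covers strictly positive values only. If the fitting routine enforces that, zero-cost subjects leave the primary analysis because of a software default rather than a decision in the plan. The winsorizing step does not help, since it acts on the upper tail.

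This matters because using any care is determined after randomization and is something the interventions may change. ICE schedules physical therapy and coach contact at every risk level (section 6.2, Table 1), IPT typically runs to eight sessions (section 6.3), and usual care has no scheduled study visits (section 6.1). If study visits are costed, the intervention arms have fewer zeros, and a users-only comparison shows a false saving. If they are not costed and they replace other care, the intervention arms may have more zeros, and a users-only comparison hides a real saving.

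The conflict with the SAP adds a second problem. An identity link estimates a difference in dollars and a log link estimates a ratio, so the scale of the primary effect is not fixed.

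**Working it through.** **1. The plan's own figure.** Inputs from section 10.2: 20% difference, 80% power, alpha 0.05 (two-sided assumed), SD 1.25 times the mean, ICC 0.01, 33 clusters (11 per arm), 10% loss.

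- Before clustering: n0 = 1.25² × (1 + 0.8²) × (1.960 + 0.842)² / 0.2² = 502.8 per arm.
- With 11 clinics per arm: 502.8 × 0.99 / (1 − 502.8 × 0.01/11) = 916.9.
- With 10% loss: 916.9 / 0.9 = 1,018.8, which is 1.3% below the stated 1,032.

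The sample size therefore reproduces closely. The present point concerns the model and does not rest on this figure.

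**2. The gamma distribution at zero.** With a coefficient of variation of 1.25, the gamma shape is 1/1.25² = 0.64. For a shape below 1 the density is unbounded as cost approaches zero, so the log-likelihood is undefined at zero.

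**3. What a GEE needs.** A GEE uses only a mean and a variance function, here variance proportional to the mean squared. It needs a positive fitted mean (which an identity link does not guarantee), not a positive response. As a check, GEEs with arm as the only covariate were fitted to simulated costs in 22 clinics and 1,848 subjects, with 187 to 577 exact zeros. Gamma/identity, gamma/log and Poisson/log all converged, used all 1,848 subjects and returned the all-subject contrast. With assumed zero shares of 10% (usual care) and 25% (intervention):

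- gamma/identity gave −147.98, equal to the raw difference in means;
- both log-link fits gave exp(−0.183) = 0.833, equal to the raw ratio;
- deleting the zeros from the same data gave a ratio of 0.96.

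This shows that zeros can be kept. It does not show what another routine would do.

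**4. Size if zeros are dropped.** The overall mean is (1 − zero share) × the mean among users. Hence

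users-only ratio = all-subject ratio × (1 − p0)/(1 − p1).

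The zero shares below are assumptions.

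| True ratio | p0 (usual care) | p1 (intervention) | Users-only ratio |
|---|---|---|---|
| 1.00 | 10% | 3% | 0.90/0.97 = 0.93 |
| 1.00 | 20% | 10% | 0.80/0.90 = 0.89 |
| 1.00 | 20% | 5% | 0.80/0.95 = 0.84 |
| 0.80 | equal | equal | 0.80 |
| 0.80 | 20% | 28% | 0.80 × 0.80/0.72 = 0.89 |
| 0.80 | 20% | 36% | 0.80 × 0.80/0.64 = 1.00 |
| 0.80 | 30% | 10% | 0.80 × 0.70/0.90 = 0.62 |

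With equal shares p the ratio is unchanged, but the dollar difference is multiplied by 1/(1 − p), for example by 1/0.80 = 1.25 at 20%.

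**5. Effect on the test, again only if zeros are dropped.** Each scenario used 3,000 simulated trials with 11 clinics per arm, 84 subjects per clinic (1,032 × 0.9/11 = 84.4) and the plan's SD and ICC. The test was a t-test on log clinic means at two-sided 0.025, with zeros removed by hand; it is not a fit of the plan's GEE. Ranges cover two runs.

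- No true difference: rejection is 9 to 10% at 10% v 3% zeros, 21 to 22% at 20% v 10%, and 45% at 20% v 5%. Keeping all subjects gives 2.3 to 2.7%.
- True 20% saving: power falls from about 66% to 23% at 20% v 28% zeros, and rejection is 2 to 3% at 20% v 36%.

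**The case against.** A reader might infer that zero-cost subjects cannot be analysed under the protocol, so that the primary comparison must be among users only. The documents do not support that. They specify a GEE, not a gamma maximum-likelihood fit, and step 3 shows that such a GEE can keep every zero. Nothing says zero-cost subjects are excluded, and the intention-to-treat sentence points against it. No GEE routine is named, so deletion cannot be read off the plan. The rejection rates in step 5 assume both the deletion and unequal zero shares.

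There may also be few zeros. The wording on zeros covers little cost as well as none. Subjects are identified and screened at a clinic visit (sections 7.2 and 7.3), and primary care visits are a counted service (section 9.1.1). If the enrolment visit is costed, zeros could nearly vanish; costing the study visits would also reduce them in the ICE and IPT arms. The plan settles neither question.

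All of this stands, and it makes the harm conditional. Two things remain. The intention-to-treat sentence fixes the arm in which a subject is analysed, but does not say how a zero response enters the cost model. And the SAP's zero-compatible model does not resolve the matter while section 10.1 names a different one for the same outcome.

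**Conclusion.** The point holds as a specification defect in a primary outcome. The protocol and SAP name different cost models with different effect scales. The protocol's choice has no mass at the zeros it describes, and no rule protects those subjects. Exclusion is possible, depending on the routine, but not established.

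If zeros were dropped, the bias in the ratio would be the factor (1 − p0)/(1 − p1), in either direction. At assumed shares of 20% v 5% with no true difference this is 0.84, a false saving of 16%; at equal shares it is 1. The actual shares are unknown and depend on which visits are costed.

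**What to change.** In protocol section 10.1, replace the gamma/identity specification for the primary cost outcome with the SAP's model: a GEE with Poisson (quasi-Poisson) variance, a log link and robust standard errors. One primary cost model then governs, and its effect measure is the relative spending difference that both documents already plan to report.

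Add to both documents: *Subjects with zero spine-related cost are included in the primary cost analysis with value zero; no subject is excluded because the cost is zero.*

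The cost is wording only, with no new data. The one downside is that a difference in dollars would need a marginal prediction step from the log-link model.

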FINAL PROTOCOL AND STATISTICAL ANALYSIS PLAN

Spine Pain INtervention to Enhance Care quality And Reduce Expenditure (SPINE CARE) – Randomized Clinical Trial

NCT03083886

10-01-2021

FINAL PROTOCOL

1. Synopsis

Low back and neck pain are among the leading causes of medical visits, lost productivity and disability. There is an urgent need to identify effective and efficient ways of helping subjects with acute spine pain while guiding practitioners towards high-value care. This trial will be a block and cluster-randomized open-label multi-centered pragmatic randomized clinical trial comparing healthcare spending and clinical outcomes for subjects with spine pain of less than three months' duration, in whom there are no red flag signs or symptoms. Subjects will be randomized to one of three treatment strategies: (1) usual primary care provider-led care; (2) usual PCP-led care with spine pain treatment directed by the Identify, Coordinate, and Enhance decision making (ICE) care model, and (3) usual PCP-led care with spine pain treatment directed by the Individualized Postural Therapy (IPT) care model. Our outcomes of interest will be spine-related healthcare utilization at one year as well as pain and functionality of the study participants.

2. Background

Direct healthcare spending on neck and back pain (spine pain) exceeds \$86 billion annually in the United States. While up to 80% of adults will experience clinically significant spine pain during their lifetimes, only a minority will progress to chronic pain with resultant high health care utilization (1–9). For the vast majority of subjects, spine pain complaints are self-limited (10–12). As a result, there is little evidence that the large amounts currently spent on spine pain has significantly improved population outcomes.

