6.2 ARM 2: PCP-led care + ICE

Subjects seeking care at a clinic assigned to this arm will receive the ICE care model through referral by their primary care provider. The ICE care model was developed by the Clinical Excellence Research Center at Stanford University based on a review of the peer-reviewed literature for adult subjects with incident neck or back pain who are not using high-dose opioid medications or receiving spine-related long-term disability payments. The care pathway is designed to take place over the course of six weeks and is intended to avoid low-value healthcare expenditures for subjects presenting with spine pain by:

1. Stratifying subjects with back or neck pain into “low” and “high” risk groups, based on the STarT Back risk assessment tool (Appendix A) (25), and directing care accordingly (Figure 1). The STarT Back tool is a validated instrument that was created to assist with the prediction of the transition of acute to chronic pain. This tool measures a subject’s physical functionality as well as their experience with pain by determining how much

their pain causes psychological distress that may magnify the disability caused by the pain itself. Baseline STarT Back tool responses have been shown to be predictive of pain intensity at six months (28).

Figure 1. Care Stratification Based on STarT Back Scoring Tool (©Keele University 01/08/07 Funded by Arthritis Research UK)

2. Directing low-risk subjects with uncomplicated back or neck pain and few psychosocial risk factors to a limited physical therapy course without additional diagnostic evaluation or specialty referral (Table 1). If subjects do not improve, they will be referred back to their primary care providers for further evaluation and treatment.
3. Referring high- and medium-risk subjects with significant biopsychosocial risk factors (i.e., a high degree of pain catastrophizing) predictive of chronicity to a novel spine team which focuses treatment on physical rehabilitation, normalization of experience, and self-management skills. The team will consist of a physical therapist serving as the

rehabilitation lead, a “Spine Coach” focusing on enabling subject self-motivation and an “ICE MD” who fulfills an advanced medical consultation role for those who do not improve after initial course of therapy. The Spine Coach is a psychology counselor trained in motivational interviewing and supportive care delivered by telephone.

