7.1 Randomization

Randomization will occur at the clinic level (i.e. subjects will be cluster randomized) in a 1:1:1 ratio to usual care, usual primary care + ICE, and usual primary care + IPT. To ensure adequate balance between the treatment arms with respect to sample size practices will be categorized into blocks of 3 based on the average number of patients with spine pain that they see in a typical week, their location, and/or their provision of other services such as urgent/walk-in care. Because of differences between the delivery networks participating in the trial, the stratification factors may differ by location. Randomization will occur within these blocks.

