7.3 Eligibility Screening

Patients presenting for care with spine pain will be informed of the study when they arrive for care and will be given a screening form to assess them for eligibility. Subjects who meet the initial eligibility criteria will be given either a written informed consent form (Vanderbilt and UBC, Appendix D) or a verbal informed consent form (HonorHealth, Appendix

D) detailing the potential benefits and risks of participating in the study, and what would be required of them. Consenting subjects will then be asked to complete the baseline surveys while waiting to be seen by their primary care provider. Their primary care provider will confirm that their symptom criteria are completed correctly and evaluate them for additional exclusion criteria that require clinical expertise (Appendix E). Subjects who meet all the inclusion and exclusion criteria will be enrolled in the study.

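### Subjects are enrolled after their clinic's arm is set, yet neither primary model has a covariate for baseline severity or risk, so both primary contrasts are exposed to selective enrolment

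*Combined protocol and SAP*

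**What the plan says.** **Design and order of events.** The Protocol synopsis describes a "block and cluster-randomized open-label multi-centered pragmatic randomized clinical trial". Protocol section 7.1 states: "Randomization will occur at the clinic level (i.e. subjects will be cluster randomized) in a 1:1:1 ratio". Clinics are grouped in blocks of three and randomized within them. The arm belongs to the clinic before the patient arrives; for ICE, section 6.2 says: "Subjects seeking care at a clinic assigned to this arm will receive the ICE care model through referral by their primary care provider". Under section 7.3, patients hear of the study on arrival, consent, and complete the baseline surveys in the waiting room. The clinic's own provider then completes screening: "Their primary care provider will confirm that their symptom criteria are completed correctly". The same provider applies the exclusions that need clinical judgement. Section 7.5 makes study-recommended visits free in ICE and IPT, while usual-care subjects pay their normal copayments.

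**Models.** Protocol section 10.1 and the SAP (Statistical considerations, 1 Analysis plan) give the same covariates for both primary outcomes: "All models will adjust for age and sex, account for the cluster and block randomized study design". Fixed effects for the three delivery networks are added. The ODI outcome is change from baseline to three months. Wider adjustment is placed in secondary analyses, described as "adjusting for unmatched confounders that remained despite randomization", with no list and no selection rule.

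**Label and available data.** Section 10.1 says: "We will report means and frequencies of pre-randomization variables separately by study arm". Its imputation model names STarT Back score, baseline ODI, length of pain and number of previous episodes. None of these is named in a primary model. Cost effects by STarT Back risk group, pain location and first episode are planned as exploratory analyses.

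**The concern.** Randomizing clinics balances clinics. It does not balance the patients enrolled afterwards if enrolment depends on the arm. Here the arm is set before anyone is approached, and the text describes neither a blinded recruiter nor identification of subjects before clinic randomization. The pressures on enrolment also differ by arm: free visits in two arms only, a daily exercise programme in IPT, and an exclusion (section 5.2) that turns on ability to take part in the intervention, which has no obvious counterpart in usual care.

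The baseline data are thus collected after randomization of the unit that was randomized, and the pre-randomization label is inaccurate. If risk mix differs by arm, the cost model has no severity term to absorb it, and the ODI change score absorbs a baseline ODI difference only in part. Block and network terms do not help: with 1:1:1 allocation in blocks of three, selective enrolment by arm occurs between clinics of the same block. At stake is whether a difference in who enrolled is read as an effect on spending or disability.

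**Working it through.** **1. The plan's own figure.** Inputs from the sample size section: 20% difference, SD 1.25 times the mean, alpha 0.05 two-sided, 80% power, 33 clusters (11 per arm), ICC 0.01, 10% loss.
- Unclustered n per arm = 1.25² × (1 + 0.8²) × (1.960 + 0.842)² / 0.20² = 502.8.
- Analysed per clinic = 1,032 × 0.9 / 11 = 84.4; design effect = 1 + 83.4 × 0.01 = 1.834.
- 502.8 × 1.834 / 0.9 = 1,025 per arm, against the stated 1,032.

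The figure reproduces to within 1%. It supplies the 20% benchmark and the precision used below. It does not bear on selective enrolment, because a larger sample does not remove that bias.

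**2. Cost, with all case-mix inputs assumed.** Let p be the medium/high-risk share in usual care, d the amount by which it is lower in an intervention arm, and k the cost of such subjects relative to low-risk subjects. With no true effect:

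ratio of mean costs = [(1 − p + d) + (p − d)k] / [(1 − p) + pk]

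At p = 0.5:
- d = 0.05, k = 1.5: 1.225 / 1.25, a 2.0% reduction.
- d = 0.10, k = 2: 1.4 / 1.5, a 6.7% reduction.
- d = 0.15, k = 3: 1.7 / 2.0, a 15% reduction.

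The middle case is a third of the 20% design difference. The last combines both extremes.

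The consequence for error rates follows from step 1. Effective n per arm = 1,032 × 0.9 / 1.834 = 506, so the standard error, as a fraction of the mean, is 1.25 × √(2/506) = 0.0786. At the planned two-sided 0.025 (critical value 2.241), a spurious difference of 6.7% raises the false-positive rate from 2.5% to about 8%, and one of 10% raises it to about 17%.

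**3. ODI, with slope and SD assumed.** Let b be the slope of three-month ODI on baseline ODI, and D the shift in an intervention arm's mean baseline ODI caused by enrolment. With no true effect, the bias in the change-score contrast is (b − 1) × D.
- b = 0.5, D = −3 (milder recruits): +1.5 points, a smaller fall, so against the intervention.
- b = 0.5, D = +3 (more severe recruits): −1.5 points, in favour of the intervention.
- For b from 0.7 to 0.3, a 3-point shift gives a bias of 0.9 to 2.1 points in size.

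A simulation (11 clinics per arm, 84 subjects each, SD 18, ICC 0.01, b = 0.5, alpha 0.025, 3,000 runs) gave the following for upward shifts of D:

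| D | False-positive rate, change score only | With baseline ODI in the model |
|---|---|---|
| 0 | 2.2% | 2.7% |
| 1 | 4.4% | 2.5% |
| 2 | 8.9% | 2.8% |
| 3 | 17.5% | 2.9% |
| 5 | 48.3% | 2.2% |

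With baseline ODI in the model the mean bias was within 0.04 points of zero. This shows what adjustment does for a measured imbalance. It says nothing about how large the imbalance is in this trial.

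**The case against.** Several points on the other side stand.

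- **Knowledge of the arm at recruitment is inferred.** It follows from clinic-level assignment, the open-label design and referral by the assigned clinic's provider, but no sentence states it. Whether patients learn the arm before consenting depends on the consent appendix, which is not in the available text.
- **The selection route is limited.** Section 7.2 recruits people already presenting with back or neck pain, so free visits may affect consent but are not shown to bring different patients in. Many exclusions are factual, and section 4 requires clinics to agree to equipoise.
- **The plan is not blind to severity.** The change score takes account of baseline ODI in part, and cost by STarT Back group is planned, though only as an exploratory analysis.
- **Modest primary adjustment with wider secondary adjustment is a recognised choice.** It is weaker here because subjects enter after allocation.

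A reader might infer three stronger things that the documents do not support. The first is that the primary models choose covariates after imbalance is seen; that choice is confined to the secondary analyses, and the primary covariates are fixed in advance. The second is that milder recruits would produce an apparent ODI benefit. A lower baseline ODI tends to bias the change score against the intervention, while lower STarT Back risk at equal ODI could act the other way, so the net direction is unknown. The third is that bias has occurred; nothing in the documents shows that.

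**Conclusion.** The point holds as one of exposure. Subjects enter after clinic allocation in an open-label design, and neither primary model has a covariate for severity or risk, although suitable variables are collected. For cost, the spurious reduction is 2% to 15% over the assumed ranges (p = 0.5, d = 0.05 to 0.15, k = 1.5 to 3), and 6.7% in the middle case. None of these inputs comes from the documents. For ODI, a 3-point baseline imbalance would bias the contrast by about 0.9 to 2.1 points for slopes of 0.7 to 0.3, with the sign depending on who enrols. The change is worth making because it is cheap and protects against measured imbalance, not because a particular bias has been demonstrated.

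**What to change.** In Protocol section 10.1 and the matching SAP analysis plan:

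1. For both primary models, prespecify age, sex, baseline ODI, STarT Back score, length of pain and number of previous episodes, in addition to the block/cluster and network terms. Pain location is optional.
2. In the secondary analyses, replace covariates defined by residual imbalance with a fixed list.
3. Relabel the data as baseline variables collected after clinic randomization.

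**Cost.** The change is to wording only: all of these variables are already collected, and they are subject-level. The models gain a few parameters. The Protocol's cost model (gamma errors, identity link) may then give negative fitted means or fail to converge. The SAP's version (Poisson errors, log link) avoids negative fitted means. The two sections contradict each other and must be reconciled in any case, and the covariate list should be settled with that decision.

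**Limit.** Adjustment cannot remove selection on unmeasured factors, such as attitude to seeking care.
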